6.7 Safety Data Analysis

A descriptive analysis of SUSAR data will be conducted by treatment allocation. The event rate is expected to be low, and thus an exact test would be an appropriate choice to perform any formal comparisons between the two groups in the proportion experiencing a SUSAR.

7 Subgroup Analyses

Consistency of the treatment effect on the primary endpoint across subgroups will be tested by including a treatment-by-subgroup interaction term (along with the relevant main effect terms) as covariates in the analysis model (as specified in Section 6.4).

The subgroups of interest are: (i) birthweight <1000 g versus 1000-1499 g; (ii) randomised ≤72 hr versus >72 hr from birth; (iii) those who received versus did not receive probiotics by 36 weeks corrected gestation (note: this is a post-baseline covariate); (iv) ≤ 28 weeks versus >28 weeks gestation at birth. Because 'probiotic use by week 36' is a post-baseline covariate, an unbiased evaluation of its role as an effect-modifier will be attempted by categorising participating sites (NICUs) into tertile subgroups according to their propensity to use probiotics, and evaluating consistency of the treatment effect across these sub-groups.

Adjusted Analyses

8.1 **Stratification Factors**

Sensitivity of results obtained from the primary analysis of the primary endpoint to adjustment for stratification factors will be explored by included them as covariates in the model (See Section 6.4).

4 5 6

7

8

9

10

11

14

15

16

1

2

3

- Randomisation is stratified by gender, birth weight (<1000 g vs ≥1000-1499 g), according to whether the baby is from a single or multiple birth, and site (NICU). Given the modest number of patients at some sites, and the degree of variation in the number of babies recruited across sites (i.e. minimum is less than 10 babies and the maximum is more than 200 babies), sites will be categorised into larger groups that have a comparable pooled primary endpoint event rate. This will be done by estimating, in a blinded fashion, the event risk at each site pooled across treatments, and deriving 'risk classification' according to tertiles. Risk classification will be used as the covariate in the
- 12

13 adjusted analyses in preference to 'individual site'.

8.2 **Treatment Compliance**

An overall treatment adherence adjusted estimate of the effect of bLF on (i) the primary composite endpoint and (ii) survival to hospital discharge will be calculated by dividing the estimated relative risk reduction (RRR) by the adherence rate as per the equation below.

17 18

$$\label{eq:RRR} \text{RRR}_{\text{adjusted}} = \frac{\text{RRR}}{100\% - (\text{bLF nonadherence \%}) - (\text{PBO nonadherence \%})}$$

19 20

The non-adherence percentage in each arm is defined as the proportion receiving less than two weeks of allocated treatment for reasons other than death.

21 22 23

24

25

26

27

A second approach for deriving treatment adherence adjusted estimates will involve clustering sites achieving comparable adherence rates into tertiles, calculating the treatment effect for each tertile, deriving a weighted combination of these individual estimates where the weights reflect the degree of adherence achieved for the tertile, and combining the treatment effect within each tertile (estimated using the analysis approach specified in Section 6.4) with its corresponding adherence weight to derive a weighted estimate.

28 29

The adherence weight (w_i) for the i^{th} tertile comprising k sites with n_i babies per site is: 30

31

$$w_i = \frac{\sum_{j=1}^{k} \{n_j \times \left(\% \ Adherence_j\right)\}}{\sum_{j=1}^{k} n_j}$$

The weighted estimate, on a log_e scale, (G) is: 32

$$G = \frac{\sum_{i=1}^{3} w_i \times \log_e(RR_i)}{\sum_{i=1}^{3} w_i}$$

The variance (V) of G will be calculated as: 33

$$V = \frac{\sum_{i=1}^{3} w_i^2 \times \text{Var}(\ln(RR_i))}{(\sum_{i=1}^{3} w_i)^2}.$$

The point estimate and 95% CI will be reported as e^G and $e^{G\pm 1.96 \times \sqrt{V}}$ respectively. 34

9 Synthesis of Trial Evidence

- 2 The evidence from LIFT will be placed in broader context in the primary reporting of results by
- 3 combining, where feasible, with evidence from other sources as described below.

4 9.1 Cochrane review

- 5 Consistent with the recommendation that reports of clinical trials should begin and end with an up-
- 6 to-date systematic review of all available randomized evidence, 5,6 data from this trial will be used to
- 7 update the most recent peer-reviewed Cochrane systematic review of trials of lactoferrin
- 8 supplementation in preterm infants. This will involve deriving an updated meta-analysis estimate of
- 9 the effect of lactoferrin on late onset sepsis, necrotizing enterocolitis and all-cause mortality, to be
- summarised in a figure in the primary reporting of results. A meta-analysis of the primary composite
- 11 endpoint used in LIFT is not currently possible because that composite endpoint has not been
- 12 reported by the other trials.

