LIFT is a multicentre phase III trial that randomises eligible babies to the experimental group receiving bLF added to breast milk or formula milk once daily, or to the control group receiving no bLF added to breast milk or formula milk. These strategies (hereafter referred to as treatments) are intended to continue until 34 weeks corrected gestation or for 2 weeks, whichever is longer, or until discharge home, if earlier.

The randomisation is performed using a centralised system that allocates patients in a 1:1 ratio via minimisation stratified by site, gender, birth weight ($<1000 \text{ vs} \ge 1000\text{-}1499\text{g}$), and according to whether the baby is from a single or multiple birth.

LIFT is masked (i.e. treatment allocation is concealed from investigators, clinicians, parents, study personnel) however a designated person (e.g. bedside nurse, pharmacist, member of milk kitchen staff, or any appropriate staff member) prepares the milk feed containing either bLF (treatment group) or nothing (control group).

- This analysis plan provides additional detail to the LIFT protocol (Version 2.0, 20JAN17, ACTRN12611000247976) on endpoint derivations and planned analyses. The health economic
- analyses described in the protocol are not detailed in this analysis plan.

2 Endpoints

analysis plan).

The primary endpoint for the study is morbidity-free survival to hospital discharge. The key secondary short-term endpoints comprise the 5 components of the primary composite endpoint.

The other secondary short-term endpoints are: time to reach full enteral feeds; number of blood transfusions; chronic lung disease; length of hospital stay; and, financial costs (out-of-scope for this

The following section provides detailed instruction on the derivation of endpoints. Any instances where the application of these instructions is unclear for a given baby will be resolved via blinded clinical review and documented.

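### The adherence-adjusted RRR in SAP Section 8.2 subtracts early stopping of control, which is not exposure to bLF and does not dilute the treatment contrast

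*SAP*

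**What the plan says.** SAP Section 8.2 plans an adherence-adjusted "estimate of the effect of bLF on (i) the primary composite endpoint and (ii) survival to hospital discharge". In words, it is "calculated by dividing the estimated relative risk reduction (RRR) by the adherence rate as per the equation below". The equation has RRR over 100% minus two terms, bLF non-adherence and "PBO nonadherence". One definition serves both terms: "The non-adherence percentage in each arm is defined as the proportion receiving less than two" weeks of what was allocated, death excepted.

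Section 1 describes what is allocated. There is a "control group receiving no bLF added to breast milk or formula milk", and the person who makes up the feed "prepares the milk feed containing either bLF (treatment group) or nothing (control group"). Treatment is meant to run to 34 "weeks corrected gestation or for 2 weeks, whichever is longer, or until discharge home, if earlier".

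Sections 6.4 and 6.5 commit to producing the adjusted estimates. For the primary endpoint they are additional to the main test; for survival to discharge they form a sensitivity analysis. Section 9.2 carries the SAP's methods into the pooled analysis with the Canadian trial.

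**The concern.** Dividing an intention-to-treat effect by an adherence figure corrects for dilution. The divisor should be the difference between arms in the proportion exposed to bLF: the share of the bLF arm that received it, minus the share of the control arm that received it. A control term belongs in the divisor only as that second quantity.

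The SAP's control term measures something else. A control baby who stops the allocated feed before two weeks, and is not then given bLF, moves from no bLF to no bLF. The contrast between arms is unchanged, yet the formula treats the baby as diluting it. The SAP neither defines control non-adherence as receipt of bLF nor counts crossover separately. The prose and the equation also disagree, since a single adherence rate is not 100% less the non-adherence of both arms.

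The same definition conflicts with Section 1 on a smaller point. Treatment properly ends at discharge home, but only death is exempted in Section 8.2. A baby who goes home before two weeks has followed the plan and is still counted as non-adherent.

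At stake is a prespecified effect size for the primary composite and for survival, which could appear in the LIFT report and again in the pooled analysis.

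**Working it through.** The SAP states no adherence rate, RRR or adjusted RRR, so there is no figure of its own to reproduce. All rates below are assumed.

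**Notation.** b = bLF-arm non-adherence; c = control-arm non-adherence as Section 8.2 defines it; x = share of control non-adherers who actually received bLF.

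- SAP formula: RRR / (1 − b − c)
- Exposure contrast: RRR / (1 − b − c·x)
- Inflation factor: (1 − b − c·x) / (1 − b − c)

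The factor exceeds 1 whenever c > 0 and x < 1, provided the SAP denominator is positive. It multiplies the RRR whatever its sign.

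**Inflation from the control term, b = c.**

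| Non-adherence per arm | x = 0 | x = 0.5 | x = 1 |
|---|---|---|---|
| 5% | 0.95/0.90 = 1.06 | 0.925/0.90 = 1.03 | 1.00 |
| 10% | 0.90/0.80 = 1.13 | 0.85/0.80 = 1.06 | 1.00 |
| 15% | 0.85/0.70 = 1.21 | 0.775/0.70 = 1.11 | 1.00 |
| 20% | 0.80/0.60 = 1.33 | 0.70/0.60 = 1.17 | 1.00 |

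**On the RRR scale, x = 0.**

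- Observed RRR 15%, 15% non-adherent in each arm: 0.15/0.70 = 21.4% by the SAP formula, against 0.15/0.85 = 17.6%.
- Observed RRR 20%, 10% in each arm: 0.20/0.80 = 25.0%, against 0.20/0.90 = 22.2%.

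**Check against a known truth.** Let the true RRR in exposed babies be 20%, with non-adherence unrelated to risk. With x = 0 the intention-to-treat RRR is (1 − b) × 20%.

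- b = c = 10%: intention-to-treat 18.0%; SAP formula 18.0/0.80 = 22.5%; exposure contrast 18.0/0.90 = 20.0%.
- b = c = 20%: intention-to-treat 16.0%; SAP formula 16.0/0.60 = 26.7%; exposure contrast 16.0/0.80 = 20.0%.

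A simulation of 8 million babies per scenario, with an assumed control risk of 25%, agreed within sampling error. It gave 22.5% against 20.0% in the first case and 26.4% against 19.8% in the second. At 10% per arm with x = 0.5 it gave 21.6% against 20.3%; with x = 1 both formulas gave 20.5%. The small excess over 20% when some controls receive bLF is a separate matter: crossover lowers the control risk that the RRR is measured against, so the expected value is R/(1 − c·x·R), for example 0.20/(1 − 0.02) = 20.4% at x = 1.

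**Limiting case.** If half of each arm stopped before two weeks and no control baby received bLF, the exposure contrast on the SAP's own threshold would be 50%. The SAP denominator would be 100 − 50 − 50 = 0, and the estimate would not exist.

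**The case against.** **The estimate is supplementary.** The primary test is the intention-to-treat Wald test of Section 6.4. No alpha or decision rule depends on the adjusted figure, and Section 8.2 also gives a second adherence method that does not use this denominator. This stands and limits how serious the point is.

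**Zero drop-in is the extreme case.** Receiving under two weeks of allocated treatment could include control babies who were given bLF, and Section 3 provides for babies analysed by the treatment they actually received. This stands as a limit on size. The error disappears only if every control non-adherer received bLF, or if there are none.

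**The net direction is open.** A reader might infer that the published adjusted benefit will be too large. The document does not support that. The two-week threshold also affects the bLF term. A baby intended for many more weeks counts as fully adherent after two, which enlarges the denominator and pulls the estimate down. Treating anything under two weeks as no exposure pulls the other way. If the intention-to-treat effect were unfavourable, the control term would magnify apparent harm.

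**Measuring adherence against the full Section 1 period could cancel the correction.** In the 15% example, suppose a further 15% of bLF babies stop between two weeks and the intended end. The corrected figure is then 0.15/(1 − 0.30) = 21.4%, the same as the SAP formula gives. Two weeks matches the minimum in Section 1 and a summary in Section 6.3, so it is a defensible threshold and the point does not extend to replacing it.

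**Early discharge is probably uncommon.** Babies weigh under 1500 g at birth, are at most 7 days old at entry, and the discharge benchmark in Section 6.6 is two months. The conflict in wording remains, but its effect is likely small and cannot be sized.

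**Conclusion.** The control term in Section 8.2 is wrong as defined and should be corrected. It subtracts early stopping of a feed that contains no bLF, where only receipt of bLF by control babies would justify a subtraction. Nothing elsewhere in the SAP repairs it.

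Taken alone, the term inflates the RRR by 6, 13, 21 or 33% at 5, 10, 15 or 20% non-adherence per arm. Those figures assume equal rates in the two arms and no bLF given to control non-adherers. At 10% per arm the inflation falls to about 6% if half of them received bLF, and to nil if all did. The true size depends on adherence data that the SAP does not give.

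Two stronger readings do not follow. The primary intention-to-treat result is not compromised. Nor is the whole adherence-adjusted estimate shown to be biased towards benefit, because the two-week cut-off acts on the bLF term as well and the net effect is not settled.

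**What to change.** In Section 8.2:

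1. Define the control term as the percentage of control babies who received bLF, set to 0% if none did. Do not subtract early stopping of control.
2. Reword the description so that the divisor is the difference between arms in receipt of bLF, to agree with the equation.
3. Exempt babies discharged home before two weeks from non-adherence, alongside deaths, so that the definition agrees with Section 1.
4. Keep the two-week threshold otherwise.

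The cost is a change of SAP wording plus one data item. Section 6.3 summarises days of treatment but not bLF received by control babies, so that count has to come from actual-treatment data such as the safety population in Section 3 already needs. The control-term change on its own moves the adjusted RRR closer to the intention-to-treat estimate, or leaves it unchanged if every control non-adherer received bLF and no other control baby did. The revised text should be in place before the pooled analysis in Section 9.2 takes over the method.

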9.2 LIFT_Canada

- 14 The protocol for the Australia and New Zealand (ANZ) LIFT trial was used to develop a similar
- 15 Canadian trial (LIFT_Canada: ClinicalTrials.gov identifier NCT03367013) with a sample size target of
- 16 N=500. Individual patient data from LIFT Canada is planned to be combined with that from LIFT (the
- 17 studies use identical electronic Case Report Forms) in order to perform pooled analyses. The pooled
- analyses will follow the methods described in this document with the following modifications: (1)
- 19 the method for aggregating sites (NICUs) described in Section 8.1 will be implemented separately for
- 20 ANZ and Canada; and, (2) evidence of heterogeneity of treatment effect across region (i.e. ANZ
- 21 versus Canada) will be evaluated on the primary endpoint.
- 22

- 23 The timing of this pooled analysis will depend on when LIFT-Canada data becomes available. This is
- 24 expected in late 2020, about 2 years after the release of LIFT Australia and New Zealand results,
- 25 based on current projections. The pooled results will be included in a further update of the Cochrane
- 26 review of enteral lactoferrin supplementation in preterm infants.

10 References:

- 2. Huque M. F. Validity of the Hochberg procedure revisited for clinical trial applications. Stat Med 2016;35:5-20.
- 3. Pocock S. J., Stone G. W. The Primary Outcome Is Positive Is That Good Enough? New Engl J Med 2016;375:971-9.
- 4. Pocock S. J., Stone G. W. The Primary Outcome Fails What Next? New Engl J Med 2016;375:861-70.

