6.4 Morbidity-Free Survival to Hospital Discharge (Primary Endpoint)

- 13 The primary analysis will be a comparison between treatment groups on the proportion of babies
- 14 experiencing the primary composite endpoint that is tested using a Wald test (with a χ_1^2 distribution)
- 15 from a log-binomial model fitted using generalised estimating equations to accommodate possible
- 16 correlation of data between siblings from multiple births. If the log-binomial model does not
- 17 converge, a logistic model will be used.

18 19

8

12

- A multiple imputation approach will be used to account for missing primary endpoint data in a
- 20 sensitivity analysis. The effect of assuming all missing values are uniformly indicative of an 'event'
- 21 (pessimistic scenario) or of 'no event' (optimistic scenario) may also be explored.

22

25

- 23 Estimates of the treatment effect on the primary endpoint that are adjusted for stratification factors
- and adherence to assigned treatment will be produced using the methods detailed in Section 8.

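### The pooled LIFT and LIFT_Canada models carry no term for trial, so the pooled effect is not a within-trial comparison; a trial term would cost almost nothing

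*SAP*

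**What the plan says.** Section 9.2 plans to combine individual patient data from LIFT with those of LIFT_Canada (target N=500). The pooled "analyses will follow the methods described in this document with the following modifications: (1". Two modifications are listed. The first is that "the method for aggregating sites (NICUs) described in Section 8.1 will be implemented separately for" the two regions. The second opens "ANZ and Canada; and, (2) evidence of heterogeneity of treatment effect across region (i.e. ANZ" and applies to the primary endpoint. Nothing else is changed.

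The main model that is carried over is in section 6.4: "The primary analysis will be a comparison between treatment groups on the proportion of babies" with an event. The test statistic comes "from a log-binomial model fitted using generalised estimating equations to accommodate possible" dependence among babies of the same birth; should that fit fail, logistic regression takes its place. Treatment is the only factor that section 6.4 implies, and the only clustering is by sibling. Section 6.5 reuses this model for the categorical secondary endpoints. Section 6.6 uses GEE models for the quantitative ones, again with no covariate named.

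The regional site groups matter only in section 8.1, a sensitivity analysis of the primary endpoint in which adjustment for "stratification factors will be explored by included them as covariates in the model". There, site is replaced by risk tertile: "Risk classification will be used as the covariate in the" models of that section.

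**The concern.** LIFT and LIFT_Canada are separate trials, each with its own randomisation, and randomisation protects the comparison inside each of them. A pooled estimate inherits that protection in full when arms are compared within trial and the results are then combined. A model with treatment alone, fitted to the merged babies, also compares treated babies in one trial with control babies in the other.

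Two things are at stake if the regional event rates differ. First, the between-trial difference stays in the error term. Second, if the analysed arms are systematically unequal in one trial, the risk difference between trials leaks into the treatment effect. The pooled results are meant to feed a further update of the Cochrane review, so the rule is worth fixing before the Canadian data arrive.

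A smaller matter sits in the adjusted model. Tertiles formed within a region rank sites relative to that region, and the SAP does not say how the two sets of tertiles are coded together.

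**Working it through.** The SAP states no power, no event rate and no sample size for LIFT, so there is no figure of its own to reproduce here.

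**Inputs from the SAP:** LIFT_Canada N=500 (section 9.2); 1:1 allocation in LIFT (section 1); two-sided alpha of 5% (section 5).

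**Assumptions not in the SAP:** LIFT N of 1,000 or 1,500; event risk of 20% or 22% in LIFT and 20–40% in Canada; a common risk ratio; sibling correlation ignored.

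**1. Bias under 1:1.** Let trial k have n_k babies per arm and control risk p_k. With a common RR, the crude ratio is Σ n_k p_k RR / Σ n_k p_k = RR, whatever the two risks are. So there is no bias.

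**2. Precision under 1:1, RR = 1.** The crude variance of log RR is 2(1/x − 1/N), with x the events and N the babies per arm in the merged data. Stratified, each trial has v = 2(1/x_k − 1/n_k), and the pooled variance is 1/(1/v_A + 1/v_C).

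Example: LIFT N=1,000, risks 20% v 40%.
- Crude: x = 500×0.20 + 250×0.40 = 200, N = 750. SE = √[2(1/200 − 1/750)] = 0.0856.
- Stratified: v_A = 2(1/100 − 1/500) = 0.016; v_C = 2(1/100 − 1/250) = 0.012. SE = √[1/(62.5 + 83.3)] = 0.0828.

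| LIFT N | Risks, LIFT v Canada | SE without trial | SE with trial | Excess (from unrounded SEs) |
|---|---|---|---|---|
| 1,000 | 20% v 20% | 0.1033 | 0.1033 | 0% |
| 1,000 | 20% v 30% | 0.0936 | 0.0928 | 0.9% |
| 1,000 | 20% v 40% | 0.0856 | 0.0828 | 3.4% |
| 1,500 | 20% v 20% | 0.0894 | 0.0894 | 0% |
| 1,500 | 20% v 30% | 0.0830 | 0.0824 | 0.7% |
| 1,500 | 20% v 40% | 0.0775 | 0.0751 | 3.1% |
| 1,500 | 22% v 30% | 0.0796 | 0.0792 | 0.5% |
| 1,500 | 22% v 40% | 0.0745 | 0.0727 | 2.4% |

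**3. Type I error.** The two-sided 5% Wald test was simulated under the null with equal arms, 40,000 runs for each case with LIFT risk 20% and Canadian risk 20%, 30% or 40%. Rejection was 4.3–5.0% without a trial term and 4.8–5.0% with stratification. The lowest value came from LIFT N=1,000 and risks of 20% v 40%.

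**4. Unequal analysed arms.** Take LIFT N=1,500 at 22%, balanced, with a share s of the Canadian babies on bLF, Canadian risk r and no true effect:

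RR = [(165 + 500·s·r)/(750 + 500·s)] / [(165 + 500(1−s)·r)/(750 + 500(1−s))]

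- s = 0.55, r = 0.40: (275/1,025)/(255/975) = 1.026
- s = 0.55, r = 0.30: (247.5/1,025)/(232.5/975) = 1.013
- s = 0.52, r = 0.40: (269/1,010)/(261/990) = 1.010
- s = 0.52, r = 0.30: (243/1,010)/(237/990) = 1.005

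Against the SEs in the table, the 55:45 shifts are ln(1.026)/0.0745 ≈ 0.34 SE and ln(1.013)/0.0796 ≈ 0.16 SE.

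**5. Tertile coding.** Two codings fit the text: three levels shared by both regions, or six region-by-tertile levels. Six levels absorb region. Three shared levels with no region term do not: if overall risks differ and each tertile holds a similar share of each region's babies, at least one label must cover two different risks.

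**The case against.** The best reply is that little turns on this. The pooled analysis is secondary, is expected about two years after the LIFT results, and leaves the LIFT primary analysis untouched. An unadjusted main model with adjustment as sensitivity is the SAP's choice throughout; LIFT's own stratification factors are left out of section 6.4 too. Canada's protocol was developed from LIFT's and the case report forms are identical, so nearly double the risk is an extreme assumption. On the figures above, the 95% limits lie about 16–17% above the point estimate (exp(1.96×0.0745) = 1.16; exp(1.96×0.0796) = 1.17), far more than any shift from a mild imbalance. All of that stands, and it is why the point is minor.

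It can also be said that region is not ignored, since by analogy with section 7 the heterogeneity model would hold a region main effect. That is fair, but it is a separate evaluation on one endpoint. It does not supply the pooled estimate and does nothing for the secondary endpoints.

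Two stronger readings are tempting and should be resisted:
- **That the plan mixes the regional tertiles.** It does not say so. It says they are formed separately, and they enter only the adjusted sensitivity analysis. What is missing is the coding.
- **That any chance imbalance between arms biases the pooled estimate.** Chance imbalance averages out over randomisation and so adds variance. A 55:45 or wider split of 500 babies has roughly a 3% chance under simple randomisation (24.5/√125 = 2.19 SD, with continuity correction). Systematic bias needs unequal allocation or differential missing outcomes. This SAP shows neither, although it does not state the Canadian ratio.

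**Conclusion.** The point holds as a minor one: a free improvement. As written, the main pooled models contain no trial term, and neither listed modification supplies one.

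Under 1:1 allocation in both trials the risk ratio is unbiased. The SE of log RR is about 0–3% larger than it need be, and the test is at most slightly conservative. The estimate would be biased only if the analysed arms were systematically unequal within a trial; an assumed 55:45 split in Canada gives a null RR of about 1.01–1.03. One route is missing data: section 2.1 always counts deaths as events but sets survivors with incomplete morbidity data to missing, and imputation is only a sensitivity analysis (section 6.4). A trial term removes the between-trial part of such a distortion, not any bias already present within a trial.

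These sizes rest on the assumed LIFT sample size and regional risks. They apply to the log-binomial model; the logistic fallback and the quantitative endpoints were not sized.

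**What to change.** Add a modification (3) to section 9.2:
- All pooled models, primary and secondary, include trial (ANZ v Canada) as a covariate or stratum.
- Heterogeneity is tested as treatment-by-trial in that model.
- The adjusted model uses risk tertile within trial (six levels), or tertile plus trial.

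Modification (1) names only section 8.1, so the same paragraph could say whether the site tertiles of sections 7 and 8.2 are also formed within trial.

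The cost is a few lines of text and one degree of freedom in the main models. No new data are needed, and the LIFT analysis itself does not change.
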